1. To assess the effects of tasimelteon 20 mg on nighttime sleep parameters as measured by Polysomnography (PSG) after an 8-hour phase advanced bedtime representative of transmeridian travel across 8 time zones.

Secondary Objectives:

1. To assess the effects of tasimelteon 20 mg on nighttime objective sleep parameters.
2. To assess the effects of tasimelteon 20 mg on nighttime and daytime subjective parameters.
3. To assess the safety and tolerability of single oral doses of tasimelteon 20 mg.

Overall Design:

This is a multicenter, randomized, double-blind, placebo-controlled, parallel pivotal trial to investigate the efficacy and safety of a single 20 mg oral dose of tasimelteon and matching placebo in healthy male and female subjects with jet lag type insomnia from an 8-hour phase advance.

Screening**V1**

IE
KSS
VAS

Evaluation**V2**

KSS KSS
VAS VAS

1 week

In-patient segment
1 day/1 night

Actigraphy and Sleep Diaries

PSG

Tasi or PBO

Pre-Sleep (baseline KSS & VAS)

Post-Sleep (KSS & VAS: 90 minutes after wake then once every 2 hrs)

EOS

CONFIDENTIAL

This material is the property of Vanda Pharmaceuticals Inc. Do not disclose or use except as authorized in writing by the study sponsor.

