7. STATISTICAL PLAN

This section describes the planned statistical analyses in general terms. A complete description of the methodology will be specified in a statistical analysis plan (SAP), which will be finalized prior to unblinding. Any changes in the statistical methods described in this protocol that occur prior to unblinding will be documented in the statistical analysis plan and will not require a protocol amendment.

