7.1. General Statistical Design

The study is a multi-center, two-arm, placebo-controlled parallel group pivotal study of the effect of tasimelteon in healthy subjects with jet lag type insomnia. Subjects will be randomized to receive either an active dose of tasimelteon 20 mg or placebo. The primary aim of the study is to ascertain whether tasimelteon is superior to placebo for the reduction of jet lag type insomnia. This study will investigate the effect of treatment on “first-night” jet lag type insomnia by measuring sleep objectively through PSG and the next-day residual effects of treatment. The primary outcome measure is total sleep time (TST) during the first 2/3 of the night (denoted by $TST_{2/3}$) following 8-hour phase advance bedtime, other

CONFIDENTIAL

This material is the property of Vanda Pharmaceuticals Inc. Do not disclose or use except as authorized in writing by the study sponsor.

objective measures (TST in other time intervals, SE, LPS, WASO, Total REM sleep time, total Non-REM sleep time, Latency to REM, and time to accumulate 30 minutes of REM sleep) and subjective next-day effects (KSS and VAS) being secondary outcomes that will provide supportive evidence. The safety and tolerability of tasimelteon will also be explored.

The randomization will be in a 1:1 ratio between the 20mg and placebo groups, and will be stratified by investigative site. The length of follow-up (a screening stage plus day into overnight assessment stage) was chosen in order to assess the “first-night effect” of tasimelteon in healthy volunteers.

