7.2. Sample Size and Accrual

The standard deviation is based on data from the tasimelteon Study VP-VEC-162-3101 comparing doses of VEC-162 and placebo in healthy volunteers in a 5 hour phase advance model. To detect a 30 minute difference in TST_{2/3} between tasimelteon-treated subjects versus placebo with a standard deviation (SD) of 75, a sample size of 150 subjects per arm provides approximately 93% power with a two-sided alpha=0.05. This sample size also provides at least 85% power to detect the difference of 28 mins (SD 80) in TST between tasimelteon treated vs. placebo group.

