7.7. Outcomes

7.7.1. Primary outcome (including definition)

One primary outcome will be considered in this study:

- TST_{2/3} which is defined as the total sleep time during the first 2/3 of night following an 8-hour phase advance bedtime, as measured by polysomnography.

The primary null hypothesis is that there is no difference in TST_{2/3} between subjects receiving tasimelteon and subjects receiving placebo. TST_{2/3} will be assessed by analysis of variance with treatment group, and clinical site as a main effect. The primary efficacy analysis will be based on the ITT population.

Details on the complete analysis can be found in the Statistical Analysis Plan.

CONFIDENTIAL

This material is the property of Vanda Pharmaceuticals Inc. Do not disclose or use except as authorized in writing by the study sponsor.

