7.7.2. Secondary outcomes

The secondary outcomes of the study are as follows:

- WASO, as measured by polysomnography. WASO is defined as the time spent awake in the period between onset of persistent sleep and lights on.
- LPS by PSG which is defined as the length of time elapsed between light-out and onset of persistent sleep. Persistent sleep is defined as the point at which 10 minutes of non-wake sleep has begun.
- The full night (as well as parts of the night) SE, defined as the total sleep time (measured by polysomnography) as a percentage of the total time spent in bed between lights off and lights on and full night TST.
- TST in other time intervals of the night, e.g. TST_{3/4} as the total sleep time during the first ¾ of the night (i.e. first 6 hours).
- Total REM sleep time, total Non-REM sleep time, Latency to REM, time to accumulate 30 minutes of REM sleep.
- The subjective post sleep assessments of sleep quality, sleep latency, and total sleep time as collected via post-sleep questionnaire.
- The next day residual effects of tasimelteon:
KSS, VAS and post-sleep questionnaire (PSQ)
- The safety and tolerability of 20 mg tasimelteon.

For the continuous secondary efficacy variables, descriptive statistics will be presented by treatment group, and the scores will be summarized and analyzed in a manner similar to that for the primary endpoint. When baseline is available for endpoint, analysis of covariance will be used by including baseline as a covariance. Categorical variables will also be summarized and evaluated. Details of the analysis will be described in the SAP.

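### Does Section 7.7.2 leave open which post-sleep KSS and VAS scores are tested, in a way that calls for a change?

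*Combined protocol and SAP*

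**What the plan says.** The design schema in the protocol synopsis labels a pre-sleep KSS and VAS as baseline and then schedules repeats: "Post-Sleep (KSS & VAS: 90 minutes after wake then once every 2 hrs". The number of repeats is not given in the text available.

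Section 7.7.2 lists KSS and VAS among the next-day residual effects. Continuous secondary variables are to be handled much as the primary endpoint is, with one addition: "When baseline is available for endpoint, analysis of covariance will be used by including baseline as a covariance". The primary model in Section 7.7.1 says that TST_2/3 "will be assessed by analysis of variance with treatment group, and clinical site as a main effect". It has no term for time or subject, as suits an endpoint measured once.

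Three further statements set the context:

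- Section 7.7.2 closes its analysis paragraph with "Details of the analysis will be described in the SAP".
- Section 7 says of the whole statistical section: "A complete description of the methodology will be specified in a statistical analysis plan (SAP), which will be finalized prior to unblinding".
- Section 7.1 gives these outcomes their role: "subjective next-day effects (KSS and VAS) being secondary outcomes that will provide supportive evidence".

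The text available contains the synopsis and Section 7 of the protocol. It contains no separate SAP text.

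**The concern.** An ANCOVA with treatment, site and baseline needs one response per subject, and here each subject has several. Three readings fit the wording: the subject's post-sleep mean, the score at one named time, or a separate ANCOVA at each time. They answer different questions and can give different results.

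The third reading also yields several p-values per scale, and Section 7 has no testing order, alpha split or adjustment for them. If the choice were made after the data were seen, a next-day claim could rest on whichever time looked best. What is at stake is how far a KSS or VAS result can be trusted as support for the primary finding.

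**Working it through.** **1. The plan's own figures.** Section 7.2 gives a 30-minute difference "between tasimelteon-treated subjects versus placebo with a standard deviation (SD) of 75", 150 subjects per arm, and "approximately 93% power with a two-sided alpha=0.05".

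- Noncentrality = 30 / (75 × √(2/150)) = 3.464. With 298 degrees of freedom, power is 93.2%, which reproduces the stated figure.
- For full-night TST (28 minutes, SD 80), power is 85.6% against at least 85% stated.

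Neither calculation uses KSS or VAS, so neither depends on how those are summarised.

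**2. False positives if every time were tested uncorrected.** The protocol gives neither the number of post-sleep times k nor the correlation r between scores. Assume k = 2 to 6 and r = 0.4 to 0.7, equal for all pairs and including the pre-sleep score. Section 7.2 states two-sided 0.05 for the sample size only; assume the same level here. The quantity is P(max |z| > 1.96) over k equally correlated normal statistics.

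Adjusting for baseline lowers the correlation between times from r to (r − r²)/(1 − r²) = r/(1 + r). So 0.4 becomes 0.286, 0.5 becomes 0.333 and 0.7 becomes 0.412.

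| k | r | Using r | Using r/(1 + r) |
|---|---|---|---|
| 2 | 0.7 | 8.4% | 9.3% |
| 3 | 0.7 | 10.9% | 13.1% |
| 4 | 0.5 | 15.6% | 17.2% |
| 6 | 0.4 | 22.6% | 24.3% |

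The span is about 8% to 24% per scale. A post-sleep mean or one time named in advance keeps each scale at 5%.

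**3. Is one summary plainly better?** Assume k = 4, r = 0.5, 150 per arm and an effect of 0.3 SD. Because Section 7.7.2 requires ANCOVA when a baseline exists, use baseline-adjusted variances (in units of the raw variance):

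- one time: 1 − 0.5² = 0.75, so d = 0.3/√0.75 = 0.346;
- mean of four: (1 + 3 × 0.5)/4 − 0.5² = 0.625 − 0.25 = 0.375, so d = 0.3/√0.375 = 0.490 for a constant effect;
- mean of four with the effect at one time only: d = (0.3/4)/√0.375 = 0.122.

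| Analysis | Constant effect | Effect at one time only |
|---|---|---|
| Post-sleep mean | 98.8% | 18.5% |
| One named time (the affected one in the last column) | 84.9% | 84.9% |
| Test at that time, Bonferroni over 4 | 68.7% | 68.7% |

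Without baseline adjustment the ordering is the same. The mean has 90.6% power for a constant effect and 13.0% for an effect at one time, a named time has 73.6%, and the Bonferroni test at that time has 53.5%. The best choice depends on the time course expected, which the protocol does not state.

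**The case for a change.** The strongest case for acting is that the missing choice matters whether or not anyone tests time by time. Under one set of assumptions, power for a short-lived effect runs from 18.5% to 84.9% depending on the summary. Section 7.1 says the study will look at next-day residual effects, so the result that counts should be fixed in advance. Doing so takes a few lines and no new data, and Section 7 says changes of method before unblinding need no protocol amendment. There is a further loose end: the synopsis also shows KSS and VAS at screening and places baseline evaluations there, so the covariate could be named more clearly.

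Much of this stands as description. The text available does not name the KSS or VAS response value, and the choice is better made blind.

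It does not show a fault in the plan. The remedy is what Sections 7 and 7.7.2 already promise, a complete SAP before unblinding, and that SAP is not available, so its silence cannot be assumed. The secondary analyses are to resemble the primary one, not to copy it, which leaves room for a repeated-measures model. The error rates in step 2 belong to an analysis the protocol never states. Correcting over times also has a price for outcomes meant to detect residual effects: in the example, power at the affected time falls from 84.9% to 68.7%. On the covariate, the schema itself labels the pre-sleep score as baseline, and an analyst would use it.

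**Conclusion.** No change to the plan follows. This is detail left to the SAP, of a kind that analysts fill sensibly before unblinding by naming one KSS result and one VAS result, adjusting for the pre-sleep score and treating the other by-time results as descriptive. Nothing in the text rules that out, and nothing commits the sponsor to uncorrected testing at each time.

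If such testing did happen, the chance of at least one false positive per scale would be about 8% to 24%. That rests on assumed values: 2 to 6 times, correlation 0.4 to 0.7, equal correlation between times, and a two-sided level of 0.05. The power comparison further assumes 4 times, correlation 0.5 and an effect of 0.3 SD; it shows a trade-off, with no option best throughout.

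The consequence is confined to supportive secondary outcomes. There is one primary outcome, and its type I error and its power (93.2% recomputed, about 93% stated) do not depend on how KSS and VAS are summarised. The conclusion would be different if the final SAP were found to test each time uncorrected and to present any significant one as a confirmed next-day effect.

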7.8. Safety Evaluation

7.8.1. Adverse Events

Adverse events will be recorded throughout the study and at early discontinuation. Adverse events and medical conditions will be coded using the Medical Dictionary for Regulatory Activities (MedDRA) coding dictionary. Treatment-emergent adverse events will be defined as those events, which are newly occurring or worsening from baseline. In all cases, only treatment emergent adverse events will be summarized.

Treatment-emergent adverse events will be summarized by presenting for each group the number and percentage of subjects having any treatment-emergent AE, having an AE in each body system, and having each individual AE. (Note: In any given category [e.g. body system] a subject will only be counted once.) Similar displays will be provided for prior (conditions ending prior to the first dose of study medication) and current (conditions present while on study medication) medical conditions.

CONFIDENTIAL

This material is the property of Vanda Pharmaceuticals Inc. Do not disclose or use except as authorized in writing by the study sponsor.

Adverse events will further be categorized by severity, relationship to study medication, and action taken. Other information collected will be listed, as appropriate. Any event starting more than 3 days after the final dose of study medication will be excluded from the above tables and only listed, unless the event caused discontinuation.

The proportions of subjects experiencing SAEs and AEs resulting in discontinuation from the study will also be summarized.

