This study will be divided into 2 phases: the screening phase and the randomization/evaluation phase. The screening phase consists of the screening visit, during which inclusion/exclusion criteria will be assessed and the baseline evaluations will be conducted. The randomization phase consists of a 1-day/1-night double-blind evaluation period in which the subject's bedtime is advanced 8 hours. The screening visit and day/night in sleep clinic will be separated by at least 1 week. Subjects meeting all entry criteria for the study will enter the randomization phase. Eligible subjects will be admitted to a sleep clinic for one day and night of evaluation. Bedtime will be determined by their habitual bedtime (as determined from screening) in the originating time zone. For example, if a subject has a habitual bedtime of 22:00 they will be put to bed at 14:00, or 22:00 in the new "time zone." A PSG will be performed throughout the night beginning prior to bedtime in the "new time zone." Following the 8-hour phase advanced sleep, subjects will complete post-sleep questionnaire, KSS and VAS assessments. During this time subjects will also be provided with breakfast and lunch. After completing all required study procedures, the subjects be discharged from the study clinic. Throughout the study the subject's sleep pattern will be monitored with an actiwatch and through subject reported sleep diaries.

[figure not shown]
[figure not shown]
Statistical Methods:

Nighttime sleep will be assessed by analysis of variance, with treatment group, clinical site, as main effect. A comparison will be made between the subjects treated with tasimelteon 20 mg and placebo. The primary efficacy analysis will be based on the ITT population.

The statistical analyses will be detailed in the Statistical Analysis Plan.

CONFIDENTIAL

This material is the property of Vanda Pharmaceuticals Inc. Do not disclose or use except as authorized in writing by the study sponsor.

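### Does the treatment-emergent adverse event definition, anchored to an unspecified baseline, let pre-dose events into the safety tables?

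*Combined protocol and SAP*

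**What the plan says.** Section 7.8.1 sets out collection, definition and display of adverse events.

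- Collection: "Adverse events will be recorded throughout the study and at early discontinuation".
- Definition: "Treatment-emergent adverse events will be defined as those events, which are newly occurring or worsening from baseline".
- Scope of the tables: "In all cases, only treatment emergent adverse events will be summarized".
- Upper limit: "Any event starting more than 3 days after the final dose of study medication will be excluded from the above tables". Such events are only listed, unless they led to discontinuation.

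No lower limit at the dose is written, and the available text (the synopsis and section 7) defines no baseline for adverse events. Elsewhere the word is used for two time points. The synopsis says: "The screening phase consists of the screening visit, during which inclusion/exclusion criteria will be assessed and the baseline evaluations will be conducted". It adds: "The screening visit and day/night in sleep clinic will be separated by at least 1 week". The study diagram in the synopsis also marks a pre-sleep baseline in the in-patient segment, for KSS and VAS only.

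Two neighbouring rules do use the dose. Section 7.6 separates prior from concomitant medications at the first dose at Visit 2. Section 7.8.1 describes prior medical conditions as "conditions ending prior to the first dose of study medication".

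**The concern.** Only treatment-emergent events are summarized, so the definition decides what every adverse event table contains. Read literally with a screening baseline, an event that begins between screening and dosing is new since baseline and would be counted, although one later dose cannot have caused it.

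The design makes this look large. Treatment is a single dose, so the countable window would hold at least 7 days before the dose and at most 3 days after it for most events. The all-treated population does not help, because it selects dosed subjects and does not filter event dates. Reported incidence would rise in both arms, the ratio between arms would move towards 1, and the difference would be less precise. Two programmers could also build different tables from the same sentence.

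**Working it through.** **Step 1: which baseline does the text favour?**

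| Element | Anchor |
|---|---|
| The term treatment-emergent (7.8.1) | Treatment |
| 3-day upper limit on the tables (7.8.1) | Final dose |
| Prior and current medical conditions (7.8.1) | First dose |
| Prior and concomitant medications (7.6) | First dose at Visit 2 |
| Baseline evaluations (synopsis) | Screening visit; adverse events not mentioned |
| Pre-sleep baseline (synopsis diagram) | Visit 2; KSS and VAS only |

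Every time rule written for safety data or for medications is counted from the dose. No sentence ties adverse events to screening. The pre-dose state at Visit 2 is the natural reading, and it gives sound tables.

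**Step 2: what would the screening reading cost?**

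The plan states no adverse event figure to reproduce. Inputs from the documents are 150 subjects per arm (7.2), a gap of at least 7 days (synopsis) and the 3-day limit (7.8.1). Assumed inputs are a background rate r of 0.5%, 1% or 2% per day, a drug effect of 5 percentage points, and recording from screening onwards.

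- Pre-dose risk: q = 1 − exp(−7r).
- Post-dose background risk: b = 1 − exp(−3mr), with m = 1 for a constant rate and m = 3 for a rate three times higher after the dose.
- Drug-arm post-dose risk: b + 0.05.
- Risk counted from screening: 1 − (1 − q)(1 − post-dose risk).
- 95% half-width of the difference: 1.96 × √[p₁(1 − p₁)/150 + p₂(1 − p₂)/150].

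Example with r = 1% and m = 1: q = 1 − exp(−0.07) = 6.8% and b = 1 − exp(−0.03) = 3.0%, so the drug arm is 8.0%. Counted from screening, placebo is 1 − 0.932 × 0.970 = 9.5% and drug is 1 − 0.932 × 0.920 = 14.2%.

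Constant rate (m = 1), placebo vs drug:

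| r per day | From the dose | Difference ± half-width | From screening | Difference ± half-width | Ratio | Widening |
|---|---|---|---|---|---|---|
| 0.5% | 1.5% vs 6.5% | 5.0 ± 4.4 | 4.9% vs 9.7% | 4.8 ± 5.9 | 4.4 → 2.0 | 33% |
| 1% | 3.0% vs 8.0% | 5.0 ± 5.1 | 9.5% vs 14.2% | 4.7 ± 7.3 | 2.7 → 1.5 | 43% |
| 2% | 5.8% vs 10.8% | 5.0 ± 6.2 | 18.1% vs 22.5% | 4.3 ± 9.1 | 1.9 → 1.2 | 46% |

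Widening is computed from unrounded half-widths.

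The share of the absolute difference kept is exp(−7r): 97%, 93% and 87%.

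With m = 3, half-widths go from 5.7 to 6.8, from 7.1 to 8.5 and from 8.9 to 10.3 points, a widening of about 17% to 20%. At r = 1%, 8.6% vs 13.6% (ratio 1.6) becomes 14.8% vs 19.4% (ratio 1.3). The pre-dose share of background events, 7/(7 + 3m), is 70% for m = 1 and 44% for m = 3.

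For a single event term the background is lower. At 0.1% per day with m = 1, 0.3% vs 5.3% becomes 1.0% vs 6.0%, and the half-width goes from 3.7 to 4.1 points.

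**Step 3: do the planned displays use these statistics?**

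Section 7.8.1 plans numbers and percentages, further split by severity, relationship and action taken. It plans no ratio, interval or test for adverse events. What the screening reading would change in the planned output is the level of the percentages, upwards in both arms.

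**The case for a change.** The strongest case for a change is that a protocol's own definition overrides the usual sense of a term, and this definition never mentions treatment. The only general statement of when baseline evaluations are done points to screening. Safety and tolerability is a stated objective of a pivotal trial, and one sentence plus a date-time filter would close the gap. The effect is not trivial in every scenario: at 0.5% per day and a constant rate, the approximate interval for the difference goes from excluding zero (5.0 ± 4.4) to including it (4.8 ± 5.9).

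The textual part stands: the sentence is ambiguous. The consequence is much weaker. It needs a reading that counts events preceding all treatment as treatment-emergent, against every dose-anchored rule around it. The interval that loses zero is not one the plan produces. Pre-dose events should be judged unrelated, which largely protects the display by relationship. The calculation also applies the full daily rate to all 7 days, although anyone who became ineligible or withdrew before dosing would not be in the all-treated population. Finally, section 7 says it describes the analyses in general terms and leaves the complete methodology to an SAP to be finalized before unblinding. The available text therefore cannot show that a dose-anchored rule is absent.

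**Conclusion.** No change follows. Section 7.8.1 leaves a term undefined, and an analyst would fill it with the pre-dose state at Visit 2, which the surrounding rules support. On that reading pre-dose events stay out of the tables.

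Only the less natural screening reading does harm, and it does so without directional bias: expected pre-dose events are equal in the two randomized arms. Its size depends entirely on assumed rates. At 0.5% to 2% per day, 87% to 97% of the absolute difference is kept. The widening of 33% to 46%, or about 17% to 20% with a threefold higher post-dose rate, applies to an interval that the plan does not call for. Neither the primary endpoint nor any planned test is affected. Naming the dose in the definition would be a harmless clarification, but the tables do not depend on it.
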